**Data collection tools:**

To protect the privacy of patients, the data collected in the study is stored completely de-identified. A code will be linked to the information provided, and answers are entered into a computer database using this code. No personal identifiers will be linked to the subject's information in the database. All of this information in the computer is password protected. The code will be linked to the subject's University of Colorado Hospital medical record number in a separate computer database. The PI will keep the surveys completed on paper in a locked cabinet.

**E. Potential Scientific Problems:**

To maximize scientific integrity this study was peer reviewed by the Colorado Department of Health & Safety (CDPHE) before receiving funding. In addition it has been reviewed in detail by scientific members of the company providing study drug, GW Research, Ltd. We do not expect problems with recruitment because of the high level of interest and publicity regarding cannabis research, especially the CDPHE funded studies. In addition, we have a large population of PD patients, since we see over 1500 PD patients in our UCH Movement Disorders clinic annually, and our 8 Movement Disorders providers also cover the VAMC and Denver Health. We do not expect problems with unblinding because the placebo will be identical and does not taste or smell different from active drug and because CBD is generally well tolerated. Also, to reduce risk of

unblinding if the dose escalation study shows that the maximal dose tolerated is less than 25 mg/kg/day, then the maximal dose for the RCT study will be reduced accordingly.

#### **F. Data Analysis Plan:**

Intention to treat concept is followed. In order to minimize data entry errors a double data entry system will be used.

If study subject agrees, the de-identified data would be shared within CDPHE Marijuana grantee consortium for future research.

#### **Stage 1: Open Label Dose Escalation Tolerability Study**

Primary Specific Aim: To confirm that the dosage regimen of CBD, in the form of Epidiolex, is safe and tolerated in 10 subjects with PD.

The primary outcome is safety and tolerability of the proposed dose of CBD and will be assessed in 4 ways:

1. Frequency of study-related adverse events at each dose level collected at standardized phone script administration and at study visits. Analysis of frequency will be mostly descriptive, and proportions and confidence intervals will be calculated. Comparisons on repeated measures can be analyzed with McNemar's test, for binary outcomes at 2 time points, or GEE models/GLMMs. Logistic or relative risk models can be used for binary outcomes, and Poisson models for counts.
2. Vital signs, orthostatic blood pressures, physical exam, EKG and labs (hematology, complete metabolic profile, urinalysis) during study visits. For vital signs and labs, means and their confidence intervals will be calculated at the two time points (baseline and the end of the open label dose escalation tolerability study), and a paired T-test will compare them. Physical exam and EKG will be descriptive.
3. Standardized assessment tools (MoCA, Anxiety short form, NPI, SCOPA-Sleep, RBDSQ, QUIP-RS, C-SSRS, Depression short form, Emotional Behavioral dyscontrol short form, Fatigue severity scale, MDS UPDRS, UDysRS, Pain Intensity 3a short form and Pain Interference 4a short form, IRLS) during study visits. Means and their confidence intervals will be calculated for each outcome at the two time points (baseline and the end of the open label dose escalation tolerability study), and paired T-tests will compare them.
4. Proportion of subjects drop out of the study due to study drug intolerance. It will be descriptive and proportions and confidence intervals will be calculated. No tests are applicable since there is nothing to compare to.

The Secondary Specific Aim is to examine the effect of CBD on severity & duration of intractable tremor and other symptoms of PD.

The secondary outcomes are tremor and the changes from baseline to the end of the open label study on cognition, anxiety, psychosis, sleep, daytime sleepiness, mood, fatigue, pain, impulsivity, other motor and non-motor PD signs, restless legs syndrome and REM sleep behavior disorder. In this open label study the aim is to obtain preliminary data on the effect of CBD on severity & duration of intractable tremor in PD. This study is not intended to be powered to obtain a clinically significant result. A paired T-test is applied to compare the data at the two time points. Analysis of binary outcomes can be performed with McNemar's test, generalized estimating equations models, and generalized mixed models.

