CBD undergoes a significant first-pass effect leading to the formation of a number of metabolites, most notably, 7-hydroxy-CBD and CBD-7-oic acid [Aguirell, S. et al. 1986; Harvey, D.J. 1990]. The half-life of CBD in humans was found to be between 18–33 hours following intravenous administration, 27–35 hours following smoking, and 2–5 days following oral administration. Bioavailability of oral and smoked CBD in humans was found to be around 6% and 31%, respectively, providing further support for a substantial first-pass effect [Aguirell, S. et al. 1986; Consroe, P. et al. 1991; Ohlsson, A. et al. 1986; Guy, GW. et al. 2004]. Oral administration of CBD (~700 mg) over six weeks to 14 Huntington's disease patients resulted in a low, narrow plasma range of 5.9–11.2 ng/mL [Consroe, P. et al. 1991]. Oral cannabis extract (10 mg  $\Delta^9$ -THC; 10 mg CBD) produced markedly lower levels of CBD (range = 0–2.6 ng/mL) at 30–120 minutes after administration and absorption was increased with food [Nadulski, T. et al. 2005a; Nadulski, T. et al. 2005b].

Human trials report that CBD decreases anxiety and causes sedation in healthy individuals, decreases psychotic symptoms in schizophrenia [Zuardi AW, et al, 2006; Leweke FM et al. 2012] and PD [Zuardi AW, et al. 2009], and may improve motor and non-motor symptoms and alleviate levodopa-induced dyskinesia in PD [Katerina Venderova', et al. 2004; Lotan I, et al. 2014; Chagas MH, et al. 2014; Zuardi AW, et al. 2008]. The ratio of THC to CBD plays a role in the preparation's therapeutic outcome: strains of cannabis with higher concentrations of CBD did not produce short-term memory impairment vs. strains with similar concentrations of THC, but lower concentrations of CBD [Englund A et al. 2013].

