## IV. Research Methods

### A. Outcome Measure(s):

#### **Stage 1: Open Label Dose Escalation Tolerability Study**

**Primary Specific Aim:** To confirm that the dosage regimen of CBD, in the form of Epidiolex recommended by the study drug manufacturer is safe and tolerated in 10 subjects with PD. Epidiolex is started at 5 mg/kg/day and is increased every 3 days by 2.5 mg/kg/day to 10 mg/kg/day. Then increase the dosage every 5 days by 5 mg/kg/day to a target dose of 20 mg/kg/day.

**Primary Outcome Measures:** The safety and tolerability of Epidiolex is measured in 4 ways:

1. By examining the frequency of study-related adverse events at each dose level.  
Adverse events are measured primarily by a standardized phone script administered at each dose level. The phone script starts with an open ended question (Do you notice any effects, good or bad, of the study drug?) and followed by a series of yes/no questions regarding adverse effects (including previously reported adverse effects of CBD and general common adverse effects of medications), and all the effects we hypothesize in the study. For each adverse and beneficial reported effect, further questions will be asked, such as when did the effect start and how is it progressing, etc. In addition, since a major dose limiting effect, per GW, is somnolence, the daytime sleepiness part of the SCOPA-sleep is included in the phone script.

The phone script is administered before each dose increase. This phone call is done by a RN, MD or an advanced practice practitioner (APP). Tolerability is judged by the appropriate clinical staff (APP, neurologist) under the supervision of the PI and sub-I (who are MDs), based on their clinical expertise.

2. By monitoring vital signs, orthostatic blood pressures, physical exam, EKG and labs (hematology, complete metabolic profile, and urinalysis) during study visits.
3. By conducting standardized assessment tools on cognition, anxiety, psychosis, sleep, daytime sleepiness, mood, fatigue, pain, impulsivity, suicidality, and motor and non-motor PD signs during study visits. In addition, since many patients with PD also have restless legs syndrome and REM sleep behavior disorder, assessments for these are also done. The assessment tools are:

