### Dose escalation strategy

Study product will be started at 5 mg/kg/day and increased every 3 days by 2.5 mg/kg/day to 10 mg/kg/day. Then increase the dosage every 5 days by 5 mg/kg/day until the subject reaches a maximum targeted dose (20 mg/kg/day) or experiences intolerable adverse effects, in which case the dose will be dropped to the last tolerated dose, for 10-15 days. Tolerability will be assessed on the third day of each dose between 5-10 mg/kg/day and the fifth day of each dose between 10-20 mg/kg/day and the subject is instructed whether or not to change the dose starting the next day. Once a subject has been on a specific dose for at least 3 days (5-10 mg/kg/day) or 5 days (10-20 mg/kg/day), that dose can be changed for less or more than 3 (5-10 mg/kg/day) or 5 days (10-20 mg/kg/day) and can be changed by a smaller increment (2.5-5 mg/kg/day) as needed for tolerability. The maximal tolerated dose is determined by the PI or co-Investigator that is an MD, based on their clinical expertise.

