#### Dose escalation strategy:

In each of the two 7-week periods, study product (CBD or placebo) will be started at 5 mg/kg/day and increased as tolerated to a maximum weight-adjusted target dose that is determined as a result of the Stage 1 study. The dose escalation strategy is the same as in Stage 1 for each treatment phase, except that subjects will take 5 mg/kg/day for 10 -15 days, and have a study visit before increasing further. The reason for a range of 10-15 days instead of exactly 10 days is to allow for some flexibility in getting subjects in for the study visit. Then the dose is escalated at 3-day intervals (with 5 mg/kg/day increased each interval) until the subject reaches the maximum target dose or experiences intolerable adverse effects, in which case the dose will be dropped to the last tolerated dose. Tolerability will be assessed on the third day of each dose and the subject is instructed whether or not to change the dose on the next day. The maximal tolerated dose is the dose at which 5 mg/kg/day higher was not tolerated on two trials. When subject achieves the maximal tolerated dose or the maximum targeted dose, they will maintain that dose for 28 +/-4 days.

Urine collection, storage and transfer for cannabis and metabolites test protocol is as described in Stage 1.

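### Stage 1 adverse-event proportions by dose level ignore time at each level, which rises from 3 to 10-15 days with dose, so a constant daily risk would read as a dose gradient

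*Combined protocol and SAP*

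**What the plan says.** Section IV.A (Stage 1, Primary Outcome Measures, item 1) defines the first of four primary safety measures: "By examining the frequency of study-related adverse events at each dose level". Section IV.F (Stage 1, item 1) gives the summary: "Analysis of frequency will be mostly descriptive, and proportions and confidence intervals will be calculated". For comparisons over repeated measures it offers McNemar's test and GEE or mixed models, and adds: "Logistic or relative risk models can be used for binary outcomes, and Poisson models for counts". It mentions no subject-day denominator, offset or other allowance for time at a level.

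The time at each level is set elsewhere. Section C.2 (Dose escalation strategy) says: "Study product will be started at 5 mg/kg/day and increased every 3 days by 2.5 mg/kg/day to 10 mg/kg/day". Steps of 5 days follow up to 20 mg/kg/day, and the maximal tolerated or target dose is held for 10-15 days. The Stage 1 Schedule of Events agrees: days 1-3, 4-6, 7-11, 12-16, then 20 mg/kg/day from day 17 to a visit on days 26-31. Stage 1 is open label with 10 subjects.

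In Stage 2 (C.3) the 5 mg/kg/day level lasts 10-15 days and escalation then goes in 3-day steps. The visit description gives 5 days at 20 mg/kg/day. At the maximal tolerated or target dose, "they will maintain that dose for 28 +/-4 days". Section IV.F (Stage 2, item 1) compares treatment with placebo at each dose level. It links binary methods to a fixed period and permits Poisson models for events over time, without stating an offset.

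**The concern.** The chance that a subject has at least one event at a level depends on the daily risk and on the number of days spent there. In Stage 1 the scheduled days never fall as the dose rises, so dose and time at risk are confounded by design. No placebo column exists to show how much of a gradient is due to time alone. A reader of the dose-level table could conclude that toxicity rises with dose, or that the brief intermediate steps are safer than the held dose, when the figures reflect only length of observation. This is the first primary measure, in the stage meant to judge tolerability level by level. Section C.2 also says that Stage 1 safety results will be studied to decide whether Stage 2 needs additional evaluations.

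**Working it through.** **The plan's own figure.** The only stated figure bearing on Stage 1 event proportions is in the Sample Size Justification: with 10 subjects, the chance of seeing no event is below 5% at a true probability of 26% and below 2.5% at 31%. Check: 0.74^10 = 4.92% and 0.69^10 = 2.45%. Both reproduce. They treat an event probability as a single number and do not refer to time at a level.

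**Constant-risk check.** Let h be a daily risk that does not depend on dose, and d the days at a level. The expected proportion with at least one event is 1 - (1 - h)^d. The documents give no h, so 1%, 2% and 5% per day are assumptions. The days come from C.2, C.3 and the Schedule of Events.

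Stage 1:

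| mg/kg/day | Days | h = 1% | h = 2% | h = 5% |
|---|---|---|---|---|
| 5 | 3 | 3.0% | 5.9% | 14.3% |
| 7.5 | 3 | 3.0% | 5.9% | 14.3% |
| 10 | 5 | 4.9% | 9.6% | 22.6% |
| 15 | 5 | 4.9% | 9.6% | 22.6% |
| 20 | 10-15 | 9.6-14.0% | 18.3-26.1% | 40.1-53.7% |

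For example, 1 - 0.98^3 = 5.9% and 1 - 0.98^15 = 26.1%. From bottom to top at 2% per day the ratio is 18.3/5.9 = 3.1 to 26.1/5.9 = 4.4, with no dose effect at all. If events are counted and divided by subject-days, the expected rate is (h × d)/d = h. That is 2 per 100 subject-days at every level when h = 2%.

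**How often ten subjects would show it.** Treating the two levels as independent, the chance that the observed proportion at 20 mg/kg/day exceeds that at 5 mg/kg/day is 53-68% at h = 1%, 70-84% at 2% and 86-96% at 5% (10 to 15 days at the top level). An exact McNemar test of the same pair at the 5% level would reject in only 0.2-1.5% of trials at h = 2%, and in 5-19% at h = 5%. In Stage 1 the risk lies in how the table is read more than in a false significant test.

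**Stage 2, within one treatment:**

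| mg/kg/day | Days | h = 1% | h = 2% | h = 5% |
|---|---|---|---|---|
| 5 | 10-15 | 9.6-14.0% | 18.3-26.1% | 40.1-53.7% |
| 10 and 15 | 3 each | 3.0% | 5.9% | 14.3% |
| 20 | 5 | 4.9% | 9.6% | 22.6% |
| Final | 28 | 24.5% | 43.2% | 76.2% |

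At h = 2% the final level gives 38.4% for 24 days and 47.6% for 32 days, the ends of the permitted window. The pattern falls and then rises. A false increase appears when the lowest dose is set against the highest, the two levels that IV.F singles out, or when a short step is set against the final dose. C.3 names 20 mg/kg/day as the Stage 2 target while the Schedule of Events runs to 25. Those passages must be reconciled, but with days of 10, 3, 3 and 28 the shape is the same.

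**Carry-over between levels.** Section III gives a half-life of "2–5 days following oral administration". By day 3 of a step, the share of that step's rise already reached is 1 - 2^(-3/5) = 34% to 1 - 2^(-3/2) = 65%. Some events caused by a short step may therefore begin at the next level.

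**The case against.** Several points on the other side stand.

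- **Stage 2 has a placebo on the same titration.** With equal daily risk and equal days at level, the expected CBD-placebo difference is zero at every level. A reader might infer that the Stage 2 safety comparison is invalid. The documents do not support that: the planned contrast is disturbed only if tolerability makes days at level differ by arm. IV.F also mentions a fixed period and events over time for Stage 2, so time is not wholly ignored there, although the model is optional and no offset is given.
- **The table does not set the Stage 2 dose.** A reader might infer that a false gradient would bias the target. Under C.1 the target is the average of individual maximal tolerated doses, rounded up, and each of those rests on clinical judgement. The stopping rule in C.7 and the added-surveillance example in C.2 count subjects, not proportions per level.
- **The highest level is not always the longest held.** That is the schedule for subjects who reach the target. A subject who does not tolerate a step drops back and spends 10-15 days at a lower dose.
- **Ten subjects give little precision.** An exact 95% interval for 2 of 10 runs from about 3% to 56%, and the plan does report intervals. They describe sampling error, though, and do not remove the confounding with time.
- **A rate per day can mislead in the opposite direction.** If events cluster soon after a dose step, the same 20% early risk gives 20/3 = 6.7 per 100 subject-days over 3 days but 20/28 = 0.7 over 28. This is a good reason to keep the proportions beside the rates.

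**Conclusion.** The point holds for Stage 1, item 1. The plan reports proportions per dose level with no time denominator, scheduled time rises from 3 to 10-15 days with dose, and there is no comparator. Under any constant positive daily risk the expected proportions rise with dose, by a factor of about 3 to 4 at an assumed 2% per day. The size depends on the assumed risk and on subjects following the schedule; the direction needs only a constant risk and the scheduled days. It is a statement about expectation, and a given sample of ten may not show it.

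In Stage 2 it holds only for comparisons between levels within a treatment. A steadily rising false dose-response across all Stage 2 levels does not follow, because the lowest dose is held for 10-15 days. The consequence is limited to how the dose-level safety tables are interpreted.

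**What to change.** In IV.F, item 1, for both stages:

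- Keep the proportions and confidence intervals, and show the days at each level in the same table.
- Add new-onset study-related events per 100 subject-days, assigned to the dose at onset, with actual days at that level as the denominator.
- Base any between-level comparison on a count model with log(days at level) as offset and robust standard errors clustered by subject.
- State two limitations: the rate assumes a roughly constant hazard and can understate early-onset events at long-held levels, and carry-over from a short step into the next level is not removed.

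The cost is a few lines of analysis-plan text and one derived variable. The home diary records dosing dates, events and dose instructions (C.2), and the phone script asks when each effect began (IV.A). No new data are collected and no dosing rule changes.

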## **Stage 2: Randomized Controlled Trial**

For the RCT the analysis will be performed in accordance with the analysis plan devised prior to unblinding. Baseline variables will be examined for equality between the two sequence groups. The primary, secondary and exploratory outcomes will be analyzed as below for both the low dose (5 mg/kg/day) and highest tolerated dose.

Primary Specific Aim: To evaluate the safety and tolerability of CBD, in the form of Epidiolex, in PD.

The primary outcome is safety and tolerability and will be assessed in 4 ways:

1. Frequency of study-related adverse events at each dose level collected at standardized phone script administration and at study visits. Analysis (frequency of study-related adverse events at each dose level in the two groups, treatment vs. placebo) will be mostly descriptive, and proportions and confidence intervals will be calculated. Contrasts involving repeated measures on the same subjects can be tested with McNemar's test (for two correlated proportions) or GEE models/GLMMs. Contrasts for independent data can be tested with standard two sample proportions test and with GLMs. Proportions, logistic regression, and relative risk regression can be applied to binary outcomes over a fixed period of time, and Poisson models can be applied to counts or events over time.
2. Vital signs, orthostatic blood pressures, physical exam, EKG and labs (hematology, complete metabolic profile, urinalysis) during study visits. For vital signs and labs, data will be analyzed as a simple two-period crossover trial. Means and confidence intervals will be presented for each group \* treatment, and for the change scores in each group. A two sample T-test will compare the means of the two groups, those in the CBD-placebo group vs. those in the placebo-CBD group, on the change scores between period 1 to period 2. The difference between the means of the two group will be equal to twice the treatment effect. Physical exam and EKG will be descriptive between the two groups (treatment vs. placebo). More complex situations, including testing for treatment \* order interaction, can be analyzed with longitudinal regression models.

3. Standardized assessment tools (MoCA, Cognition assessment battery, Anxiety short form, NPI, SCOPA-Sleep, RBDSQ, QUIP-RS, C-SSRS, Depression short form, Emotional Behavioral dyscontrol short form, Fatigue severity scale, MDS UPDRS, UDysRS, Pain Intensity 3a short form and Pain Intensity 4a short form, IRLS, PDQ-39 and EQ-5D-5L) and lab tests, the data will be analyzed as a simple two-period crossover trial. Means and confidence intervals will be presented for each group \* treatment, and for the change scores in each group. A two sample T-test will compare the means of the two groups, those in the CBD-placebo group vs. those in the placebo-CBD group, on the change scores between period 1 to period 2. The difference between the means of the two group will be equal to twice the treatment effect. More complex situations, including testing for treatment \* order interaction, can be analyzed with longitudinal regression models.
4. Proportion of subjects drop out of the study due to study drug intolerance. Analysis (proportions of subjects drop out of the study due to study drug intolerance in the two groups, treatment vs. placebo) will be mostly descriptive, and proportions and confidence intervals will be calculated. Proportion differences between groups can be compared with the standard test.

The difference between the mean change scores of the two group will be equal to twice the treatment effect. We will test the null hypothesis of no treatment effect. To test and control for a possible time/order effect, longitudinal regression models will be fit with a time/order variable included.

Secondary Specific Aim is to examine the effect of CBD on severity & duration of intractable tremor in PD.

For the secondary outcome, tremor, the data will be analyzed as a simple two-period crossover trial. Means and confidence intervals will be presented for each group \* treatment, and for the change scores in each group. A two sample T-test will compare the means of the two groups, those in the CBD–placebo group vs. those in the placebo–CBD group, on the change scores between period 1 to period 2. The difference between the means of the two groups will be equal to twice the treatment effect. We will test the null hypothesis of no treatment effect. To test and control for a possible time/order effect, longitudinal regression models will be fit with a time/order variable included. Covariates, such as age or baseline disease severity (H&Y) may be adjusted for as covariates, especially if unbalanced between the sequence groups.

**Exploratory Outcome Measures:** The effects of CBD on cognition, anxiety, psychosis, sleep, daytime sleepiness, mood, fatigue, pain, impulsivity, and motor and non-motor PD signs, restless legs syndrome, REM sleep behavior disorder and quality of life are evaluated using the aforementioned assessment tools. The change from baseline to 10th day of 5 mg/kg/day (low dose analysis) and from baseline to the maximum tolerated or targeted dose is compared.

Exploratory analyses: (1) To study the effect of CBD on cognition, anxiety, psychosis, sleep, daytime sleepiness, mood, fatigue, pain, impulsivity, other motor and non-motor PD signs, restless legs syndrome and REM sleep behavior disorder, (2) To evaluate the effects of CBD on these conditions at a low dose.

Exploratory outcomes includes assessments of cognition, anxiety, psychosis, sleep, daytime sleepiness, mood, fatigue, pain, impulsivity, other motor and non-motor PD signs, restless legs syndrome and REM sleep behavior disorder. The effect of CBD at both a low dose (5 mg/kg/day) and the maximum tolerated or targeted dose is studied. Continuous outcomes will be analyzed in the same way as tremor. Transforms or non-parametric methods will be applied as necessary. Non-continuous outcomes will be analyzed with generalized estimating equations models, and generalized mixed models, and with McNemar's test for binary outcomes.

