#### **C.5 Randomization and drug dispensation:**

Patients who consent will be stratified by age (45 – 60 and 61-78) and disease severity (H&Y 1 – 2.5, 3 – 5) and divided into blocks of a few patients each, depending on order of recruitment. Equal numbers from each block will be assigned to each of two sequence groups. One group will receive the control first and the treatment second, and the other group will receive the treatment first and the control second. Since all subjects receive both treatments randomization and stratification are less critical than in studies with fixed treatment groups, unless order effects are important or an expectedly large number of patients drop out.

The study drug, Epidiolex, and matching placebo will be provided by GW Pharmaceuticals. GW will ship the drug according to British and US regulations. Initially enough study drug will be provided for the Stage 1 open label study, and replenishment shipments will follow. [name], the PI, will obtain a Schedule 1 license and all procedures of drug handling will be according to DEA specifications. Briefly, designated study personnel will receive the study drug, store it, measure and label it ([name] and her fellow) and dispense to the subject (study coordinator).

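### Stage 2 binary outcomes have no fixed period-adjusted analysis: McNemar's test, one of the named options, ignores period and is biased if the two sequences supply unequal numbers of pairs

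*Combined protocol and SAP*

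**What the plan says.** Section C.5 randomises Stage 2 subjects in equal numbers to CBD-then-placebo or placebo-then-CBD. It treats randomisation and stratification as less critical here "unless order effects are important or an expectedly large number of patients drop out".

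In section F (Data Analysis Plan, Stage 2), the test for vital signs, labs, rating tools and tremor compares the sequence groups: "those in the CBD-placebo group vs. those in the placebo-CBD group, on the change scores between period 1 to period 2". That contrast removes any period effect common to both sequences. Continuous exploratory outcomes are to be handled as tremor is.

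Binary outcomes are treated differently. Under primary item 1 the adverse-event analysis "will be mostly descriptive, and proportions and confidence intervals will be calculated", and then "Contrasts involving repeated measures on the same subjects can be tested with McNemar's test (for two correlated proportions) or GEE models/GLMMs". For the exploratory outcomes: "Non-continuous outcomes will be analyzed with generalized estimating equations models, and generalized mixed models, and with McNemar's test for binary outcomes".

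After the four primary items a further paragraph adds: "To test and control for a possible time/order effect, longitudinal regression models will be fit with a time/order variable included". It follows statements about mean change scores and does not mention binary outcomes.

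**The concern.** McNemar's test compares discordant pairs across the whole sample, without regard to which treatment came first. It suits Stage 1, a single-arm study at two time points, where the plan also names it. In a two-period crossover it mixes the treatment effect with any period effect unless both sequences supply the same number of pairs.

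Both conditions for trouble are plausible, although the documents quantify only dropout. Adverse events are elicited by a repeated prompted phone script, so reporting could drift between periods. Under the participant stopping rules in C.7, a related grade 3 or 4 event ends treatment. A CBD-first subject who leaves in period 1 has no placebo period and forms no pair. A placebo-first subject who leaves on CBD already has placebo data. Intolerance can therefore unbalance the pairs.

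Adverse-event frequency is the first component of the primary outcome. A biased paired contrast would shift the reported CBD-placebo difference even if little weight is put on the p-value.

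**Working it through.** **1. The plan's own power figure.** No power is given for any binary outcome. The only Stage 2 calculation is for tremor (Sample Size Justification): n = 38, SD of differences 3, effect 1.625, alpha 0.05.

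- Paired t-test: noncentrality 1.625 × √38 / 3 = 3.34; power 90.2%.
- Sequence-group t-test, 19 per sequence, difference 2 × 1.625 = 3.25: noncentrality 3.25 / (3 × √(2/19)) = 3.34; power 90.1%.
- Dropout: 38 / 0.9 = 42.2, rounded up to 43.

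The stated figures reproduce, and for tremor the sequence-group form costs almost nothing.

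**2. Size of the bias.** Let c1, c2 be the CBD event probabilities in periods 1 and 2, and p1, p2 those on placebo. Let n1 and n2 be the complete pairs in the CBD-first and placebo-first sequences.

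- McNemar's implied risk difference: [n1(c1 - p2) + n2(c2 - p1)] / (n1 + n2)
- Sequence-group estimate (half the difference in mean period 1 minus period 2 scores): ½[(c1 - p2) + (c2 - p1)]
- First minus second: (n2 - n1) / [2(n1 + n2)] × [(c2 - c1) + (p2 - p1)]

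The gap is zero if n1 = n2 or if there is no period effect. Otherwise its sign depends on both.

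Take 48 subjects, 24 per sequence. Ten percent is 4.8, so 5 are lost. If all 5 are CBD-first, the pairs are 19 and 24.

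- No CBD effect, event rate falling from 44% to 22%: 5/86 × 2 × (-0.22) = -0.026, where the truth is 0.
- A second set of assumed rates, c1 = 0.500, c2 = 0.303, p1 = 0.303, p2 = 0.156: the sequence-group estimate is ½(0.344 + 0) = 0.172; McNemar's is (19 × 0.344 + 24 × 0)/43 = 0.152. Simulation gave 0.173 and 0.153.
- The same setting with events rising in period 2 (simulated): McNemar 0.218 against 0.196.

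**3. Power.** These rates are assumptions, since the documents give none: placebo 44% and CBD about 73% in period 1, and a subject random effect with SD 1 on the logit scale. A period log-odds of -0.7 takes placebo to about 30% in period 2, and -1.2 to about 22%. Each setting used at least 40,000 simulated trials, two-sided 0.05. The comparator is a two-sample test of period 1 minus period 2 scores. Ranges cover repeat runs.

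| Pairs, CBD-first / placebo-first | Period log-odds | McNemar | Sequence-group |
|---|---|---|---|
| 22 / 22 | -0.7 | 86% | 86-87% |
| 22 / 22 | -1.2 | 82-83% | 84-86% |
| 19 / 24 | -0.7 | 79-81% | 83-86% |
| 19 / 24 | -1.2 | 70-74% | 81-84% |
| 17 / 24 | -0.7 | 76-77% | 82-84% |
| 17 / 24 | -1.2 | 66-67% | 81-82% |
| 24 / 19 | -0.7 or -1.2 | 88-89% | 84-85% |

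With no period effect the sequence-group test is about 1 point lower. The 24/19 row is not a true gain, because McNemar's estimate is there biased toward harm.

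**4. Second set of assumptions.** Placebo about 30% in period 1, CBD log odds ratio 1.0:

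- 24/24 pairs: 48.5% against 51.0% (period log-odds -1), and 54.2% against 56.8% (+1).
- 19/24 pairs: 35.0% against 46.1% (-1), and 58.5% against 51.4% (+1).
- 24/19 pairs: 52.5% against 46.5% (-1), and 39.8% against 51.2% (+1).
- 19/24 pairs, no CBD effect: McNemar gives false harm signals in 1.1% (-1) or 3.5% (+1) of trials, against a nominal 2.5%.

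**The case against.** A reader might infer that Stage 2 binary outcomes simply go to McNemar's test, and that it misses CBD harm which the plan's own sequence-group comparison would detect. The documents do not support that.

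- The wording for adverse events is permissive, GEE and mixed models are named beside McNemar's test, and the analysis is mostly descriptive.
- The sequence-group comparison is written for continuous measures and not for adverse events.
- The bias has no fixed direction; the same mechanism can exaggerate harm.
- In the second set of assumptions the sequence-group test itself finds harm only about half the time, so it is too strong to set one test as missing harm and the other as detecting it.

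The time/order sentence could also be read as covering all four primary items, since GEE and mixed models can carry a period term. That reading is possible but not secure, and it would leave McNemar's test as a listed alternative with no rule for choosing.

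The 19/24 split is a severe case, with every dropout in one sequence, and nothing in the documents establishes a period effect of this size. With CBD assumed at 71% in period 1 and a milder 22/24 split, power is 82% against 84% (-0.7) and 76% against 82% (-1.2).

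Two limits on the remedy also stand. A complete-pair test does not cure informative dropout: removing five CBD-first subjects who had period 1 events and higher susceptibility lowered the sequence-group estimate from 0.267 to 0.250 and its power from 79% to 72%. The power gain also depends on the form of the test: the exact Mainland-Gart test was no more powerful than exact McNemar (27.7% against 27.4% at 19/24, period log-odds -1, CBD log odds ratio 1.0).

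**Conclusion.** The point holds as a cheap improvement. The plan removes period from its continuous contrasts but names, for binary ones, a test that cannot, beside models whose period term is not stated.

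With equal sequences the cost is about 1 to 3 points of power and no bias. With the planned dropout concentrated in one sequence and a sizeable period effect, power moves by roughly 3 to 12 points in either direction, and the risk difference by about 0.02 to 0.03. These sizes rest on assumed event rates, period effects and subject variance, and on dropout unrelated to outcome. The existence of the bias, and the dependence of its direction on the losses and the period effect, follow from the formula and not from those values.

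The sample size text plans 48 subjects and the design section 50; the conclusion does not depend on which applies.

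**What to change.** In section F, Stage 2, under primary item 1 and under the exploratory outcomes, replace McNemar's test for CBD versus placebo contrasts with one pre-specified period-adjusted binary analysis. Either of these would do:

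- a GEE or mixed model with treatment and period terms, which also uses subjects observed in only one period; or
- a comparison of the sequence groups on period 1 minus period 2 scores of +1, 0 or -1 (Prescott's test), reporting half the mean difference, with its confidence interval, as the risk difference.

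If the time/order sentence is meant to cover binary outcomes, say so there. Keep McNemar's test for the Stage 1 comparisons of two time points. Keep dropout for intolerance as the separate analysis in item 4, since neither McNemar's nor Prescott's test corrects for it.

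The change needs no new data or visits. The cost is about 1 point of power if there is no period effect.
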